Primary efficacy parameter: Live birth rate

Secondary efficacy parameters: Singleton live birth rate, ovulation rate, cycles to first ovulation, cycles to conception (defined by positive serum HCG), abortion rate, cycles to pregnancy (defined by detection of fetal heart beat), and weeks from pregnancy to live birth.

NICHD Reproductive Medicine Network
PPCOS-Pregnancy in Polycystic Ovary Syndrome Protocol
Statistical Analysis: The primary analysis will use an intent-to-treat approach to

examine differences in the live birth rate among three treatment arms. A chi-square test will be used to compare the proportion of live births between the combined clomiphene citrate/Metformin XR group versus the group of either Metformin XR alone or clomiphene citrate alone that has the higher proportion of live births. If this comparison is not significant a chi-square test will be used to compare the proportion of live births between the Metformin XR alone versus clomiphene citrate alone. Logistic regression models will be used in secondary (or supplemental) analyses to evaluate the predictive value of treatment condition, clinical site, prior exposure to either clomiphene citrate or metformin XR, body mass index, and other explanatory variables on binary outcomes (e.g., , abortion, ovulation). Cox proportional hazards models and a Kaplan-Meier method will be applied to compare time to event (eg. Cycles to first ovulation, cycles to pregnancy) between the treatment groups. An interim analysis, incorporating an O'Brien-Fleming adjustment, will be performed when half of the study participants have completed treatment.

Anticipated time to completion: A total of three to four years will be required to complete the study; two year enrollment period, 30 week treatment period, with one year additional observation to determine pregnancy outcomes. This will be accomplished by enrolling 50-90 PCOS women per center over the two-year enrollment period. There are 12 centers currently participating. Other centers may be added.

II. BACKGROUND

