Ideally, the threshold for identifying a minimum difference between treatments is informed by prior data on a variety of factors important for decision making, including efficacy in randomized trials, effectiveness in clinical practice, side effects, patient values for benefits, side effects, and risks of each treatment, health-related quality of life, and costs. Unfortunately, data that would allow estimation of these factors for the clinical situation addressed by this protocol are unavailable.

In the absence of specific data, we assume that any combination of two or more drugs must be superior to either agent alone in order for the combination to be considered the "best" treatment. In other words, given that combination therapy inevitably will cost more than either agent alone, that it will carry the risks of the side effects of both agents, and be less convenient for patients than either alone, the combination of metformin plus clomiphene citrate must be superior to either agent alone by some amount in order for it to become the treatment of choice.

We propose that an absolute difference in live birth rates after 6 months of therapy of **15%** is clinically important.

3. Null Hypotheses

NICHD Reproductive Medicine Network
PPCOS-Pregnancy in Polycystic Ovary Syndrome Protocol

(A) The live birth rate after 30 weeks of therapy with the combination of metformin plus clomiphene citrate is not different from the live birth rate after either metformin alone or clomiphene alone.

(B) The live birth rate after 30 weeks of therapy with metformin alone is not different from the live birth rate after clomiphene alone.

4. Possible Study Outcomes and Interpretation:

a) Null hypothesis (A) is rejected

If the null hypothesis is rejected, we expect that combination therapy is superior to either agent alone, and, barring significant differences in adverse events, combination therapy becomes the treatment of choice.

b) Null hypothesis (A) is accepted, but null hypothesis (B) is rejected

If the difference between combination therapy and one of the single agents is less than 15%, then null hypothesis (A) is accepted. If the observed difference between the single agents is greater than 15%, we expect that metformin would become the treatment of choice, barring substantial differences in adverse events. (This also allows for the possibility that Metformin alone will be at least 15% more effective than clomiphene alone).

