c) The null hypothesis is accepted, but no statistically significant differences are observed between any of the treatments.

If the observed differences between all three agents are less than 15%, then the choice of initial treatment will likely be based on side effects, convenience, costs, etc.

Although this trial will not be able to definitively answer that issue, data collected from this study will allow planning of additional studies to address issues of cost-effectiveness, health-related quality of life, patient preferences, etc.

NICHD Reproductive Medicine Network
PPCOS-Pregnancy in Polycystic Ovary Syndrome Protocol
Given these considerations, at most two comparisons are needed

- Scenario 1: Point estimate of live birth rate with combination therapy higher than with either agent alone

Comparisons: (1) Combination therapy vs. highest single agent, (2) single agents to each other.

Rationale: In order to be preferred, combination therapy needs to be superior to both agents. If combination is not superior to the agent with the highest live birth rate, demonstration of superiority to the other agent is not clinically meaningful. Direct comparison of single agents becomes the critical comparison for decision making.

- Scenario 2: Combination therapy less effective than one of the single agents

Comparisons: 1

Rationale: Given cost, complexity, side effects, etc., combination therapy must be demonstrably more effective than single agent therapy in order to be clinically preferable. In this scenario, only the comparison between the two single agents is meaningful.

5. Sample Size Calculations

Primary Endpoint - Live Birth Rate

Assumptions

- 15% absolute difference considered to be clinically meaningful
- 15% dropout rate
- Overall alpha level = 0.05, two-tailed test
- Two planned comparisons

NICHD Reproductive Medicine Network
 PPCOS-Pregnancy in Polycystic Ovary Syndrome Protocol

1) Lowest rate vs. second lowest rate

2) Second lowest rate vs. highest rate

- χ^2 test for differences in proportions
- Best estimated live birth rates:
 - 1) Metformin alone: **30%**
 - 2) Clomiphene alone: **25%**
 - 3) Metformin + clomiphene citrate: **45%**

Parameters for sample size calculations:

- Alpha = **0.025**, two-tailed tests since two planned comparisons
- Beta = **0.20**, or 80% power

Sample Size

Treatment 1 (live birth rate)	Treatment 2 (live birth rate)	Required Sample Size	Sample Size with dropout adjustment	Total Sample Size

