The completed case report forms (CRF) will follow these guidelines: All data on the CRFs will be entered in ink. No data entry in the original CRF may be deleted or corrected by erasure, use of ink eradication fluid or any other such means. When a data entry is in error, draw a single line through the erroneous entry (the original data must remain discernible) and indicate the correct data in whatever way is appropriate. These changes should be initialed by the P.I. or designated study coordinator. Validity of data

NICHD Reproductive Medicine Network
PPCOS-Pregnancy in Polycystic Ovary Syndrome Protocol
recorded on CRFs during each patient visit will be attested to by one of the investigators
by a dated signature on an appropriate CRF page. All questions should be answered.
Data management will be as per DCC guidelines.

R. Competency to perform procedure/tests in the protocol

The principal investigator will be responsible for ensuring that laboratory and patient tests performed as part of the study are performed by competent personnel. These tests include semen analysis, ultrasonography of the pelvis, sonohysterography and/or hysterosalpingography of the uterus and fallopian tubes. The criteria for determination of competency may vary between sites in the study.

V. DATA ANALYSIS

All statistical tests will test non-directional hypotheses. The level of significance will be set at 0.05 for primary analyses and 0.05 for secondary analysis. An intent-to-treat principle will be employed during the primary analysis of the primary efficacy and safety measures. For the intent-to-treat analyses, randomized women will be included regardless of whether or not the patient received the assigned treatment, the patient was compliant with the treatment plan, and/or the treatment was administered according to randomization assignment.

A. Primary Efficacy Measure

Primary Analysis: A live birth will be defined as delivery of any viable infant. The primary analysis of the primary endpoint will include the following procedures. A chi-square test for equal proportions will be performed to evaluate whether live birth rate in Metformin/clomiphene group is the same as one in the group of either Metformin alone or clomiphene alone that has the higher live birth rate. If the test is not significant, a standard chi-square test will be used to examine differences in proportions in live births

NICHD Reproductive Medicine Network

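### The rule that metformin vs clomiphene is tested only if the combination test is not significant conflicts with the protocol's own hypotheses, power statement and Scenario 2

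*Protocol*

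**What the plan says.** The synopsis (Statistical Analysis) compares the combination with whichever single agent has the higher live birth rate, and continues: "If this comparison is not significant a chi-square test will be used to compare the proportion of live births" between metformin and clomiphene. Section V.A repeats the condition: "If the test is not significant, a standard chi-square test will be used to examine differences in proportions in live births". It sets 0.05 for every test in the primary analysis, and section V makes all tests non-directional.

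The planning sections read differently:

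- IV.B.3 gives null (B) with no condition: "The live birth rate after 30 weeks of therapy with metformin alone is not different from the live birth rate after clomiphene alone".
- IV.B.4, Scenario 1 (combination has the highest point estimate), lists two items: "Comparisons: (1) Combination therapy vs. highest single agent, (2) single agents to each other". Its rationale adds that, if the combination is not superior to the better agent, "Direct comparison of single agents becomes the critical comparison for decision making".
- IV.B.4, Scenario 2 (combination less effective than one of the single agents), allows one comparison and says that only metformin vs clomiphene matters.
- IV.B.4(a) says that when null (A) is rejected, "barring significant differences in adverse events, combination therapy becomes the treatment of choice".
- IV.B.5 sets alpha at 0.025, "two-tailed tests since two planned comparisons", with 80% power for a 15-point difference. The planning rates are 45% (combination), 30% (metformin) and 25% (clomiphene).

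**The concern.** Sections IV.B.3 and IV.B.5 plan and size two tests. The synopsis and V.A perform only one whenever the first is significant in either direction. A reader of IV.B.5 would take it that a 15-point difference between metformin and clomiphene has at least an 80% chance of being shown. Under the gate, that chance depends on how the combination performs.

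Two situations suffer. If the combination wins but adverse events set it aside, as IV.B.4(a) allows, the choice returns to the single agents without a primary test between them. If the combination is significantly worse than the better single agent, the gate closes in the one situation where Scenario 2 calls the single-agent comparison the only useful one.

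**Working it through.** **Inputs.** From IV.B.5: 197 per arm before dropout, 226 per arm after, 0.025 two-sided per comparison, 15-point difference, planning rates 45/30/25%. From V.A: the gate, and 0.05 per test. Rates below are in the order combination/metformin/clomiphene.

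**The plan's own figure.** n = [z(1−α/2)·√(2p̄(1−p̄)) + z(0.80)·√(p1(1−p1)+p2(1−p2))]² / (p1−p2)². With p1 = 0.45, p2 = 0.30, p̄ = 0.375 and α = 0.025: [2.241 × 0.685 + 0.842 × 0.676]² / 0.0225 = 196.7, so 197, as stated. The dropout step matches multiplication by 1.15 (197 × 1.15 = 226.55; stated 226).

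**A bound.** Under the gate, (B) can be rejected only if (A) is not, so P(reject B) ≤ 1 − P(A significant). With 84% for (A), this is at most 16%.

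**Simulation.** Binomial arms, uncorrected two-sided chi-square, 1,000,000 trials per setting, no interim look. A = combination vs the better observed single agent. B = metformin vs clomiphene. Both are at 0.025.

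| True rates (%) | n/arm | A significant | B rejected, gated | B rejected, always tested |
|---|---|---|---|---|
| 50/35/20 | 226 | 84% | 16% | 91% |
| 50/35/20 | 197 | 78% | 21% | 87% |
| 55/40/25 | 226 | 84% | 16% | 88% |
| 55/40/25 | 197 | 77% | 23% | 83% |
| 45/45/30 | 226 | 3% | 84% | 86% |
| 45/45/30 | 197 | 2% | 79% | 80% |
| 30/45/30 | 226 | 86% (combination worse) | 9% | 86% |
| 45/30/25 (planning rates) | 226 | 85% | 6% | 15% |
| 45/30/25 (planning rates) | 197 | 79% | 6% | 13% |

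At 0.05 per test, as in V.A, with 226 per arm: 50/35/20 gives 10% gated against 95% always tested. At the planning rates (A) is significant in 91% of trials, so (B) is run in 9%.

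**Familywise error.** With all three rates equal, the event that at least one test rejects is the same with or without the gate: either A rejects, or A does not and B does. At 30% in each arm it is about 4.7% at 0.025 per test and about 9.2% at 0.05 per test. With 0.05 for A and 0.025 for B it is about 7%.

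**The case against.** The gate is a reasoned decision order. IV.B.4 says that at most two comparisons are needed, explains why the single-agent comparison becomes critical when the combination is not superior, and lists no outcome in which (A) is rejected and (B) is then examined. The efficacy hypothesis in the synopsis and III.A concerns the combination only. On this view IV.B.5 merely lacks a sentence saying that (B) is conditional. V.A also plans logistic regression of live birth on treatment, so an exploratory single-agent contrast remains available.

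Much of this stands. A reader might infer that the trial cannot deliver its 80% power for (B) at all. The documents do not support that: when the combination merely equals the best single agent, gated power is 79-84% for 45/45/30. A reader might also infer that the gate spoils the sponsor's expected result. At 30% vs 25%, however, (B) would be rejected in only about 15% of trials even ungated, against about 6% gated. Nor is the 0.025 share wasted by the gate, because the gated procedure needs that split to hold 5%. The settings with 15 points at each step are illustrations: no section assumes that pattern for the three arms.

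What the objection does not answer is that null (B) and its power are stated without condition, that the gate yields no error control in return, and that the two-sided gate contradicts Scenario 2. The last point is a conflict with the protocol's own decision logic.

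**Conclusion.** The inconsistency is real and limited in scope. The 80% for metformin vs clomiphene holds, within tolerance, when the combination is about equal to the better single agent. It does not hold when the combination is truly about 15 points better (about 16% at 226 per arm, 21-23% at 197), or when it is about 15 points worse than the better agent (about 9% at 226 per arm for 30/45/30). The gain from removing the gate at the planning rates is small, about 9 percentage points at 226 per arm.

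These figures assume 0.025 per test, uncorrected chi-square tests, the stated rates as true rates in the analysed women, and no interim look. The sample sizes 197 and 226 bracket the effect of dropout. The 0.05 in V.A against the 0.025 in IV.B.5 is a separate and more serious conflict, and any repair here depends on resolving it.

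**What to change.** Preferred: delete the condition in the synopsis and V.A, run both comparisons in every case at 0.025 each, and change the 0.05 for primary tests in V.A to 0.025 for both. Changing only the second test would leave about 7% familywise error when all rates are equal. The general statement of 0.05 at the start of section V and the critical value in the V.F stopping rule should then be aligned. This needs no more patients and adds one reported test. Relative to V.A as written, the first test's power at the planning rates with 226 per arm falls from 91% to 85%, still above the 80% for which IV.B.5 sized it.

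If the gate is kept: restate IV.B.3 to IV.B.5 so that null (B) and its 80% power apply only when the combination does not differ significantly from the better single agent, and reconcile the gate with Scenario 2, for instance by closing it only when the combination is significantly better. The alignment to 0.025 is still needed. The cost is wording only.

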clomiphene citrate alone, metformin achieved a significantly higher ovulation rate than clomiphene citrate alone (20). These women were only followed for 35 days on metformin, but achieved a 35% ovulation rate in this period (20). Studies which systematically examined menstrual regularity in PCOS women on metformin over a longer period of time have noted substantial improvement. Regular cycles, suggestive of monthly ovulation, have ranged from 69-96%(17;21;22). Few studies have addressed the issue of pregnancy in PCOS women on metformin and these have been observational and limited by a small sample size. (17;23) A more complete discussion of these trials is found in discussion of the power analysis below under IV B. Sample Size.

The preliminary evidence suggests that metformin in PCOS women is well tolerated, results in spontaneous ovulation, and is without known adverse effects during early pregnancy. Recently a new sustained release form of metformin, metformin XR with brand name Glucophage XR, has become available, and while similarly efficacious in the treatment of type II diabetes as metformin, it has a more favorable side effect profile. There are no published reports of the efficacy and tolerability of metformin XR in women with PCOS.

III. Objectives

A. Primary Research Hypotheses

The primary hypothesis is that improving insulin sensitivity and inappropriate gonadotropin secretion in infertile women with polycystic ovary syndrome (PCOS) with metformin and clomiphene citrate is more likely to result in a live birth than treatment with Metformin alone or clomiphene alone.

NICHD Reproductive Medicine Network
PPCOS-Pregnancy in Polycystic Ovary Syndrome Protocol
Primary Outcome Measure

The primary outcome measure is the presence/absence of a live birth during the study period. The primary analysis of live birth rate within the three treatment conditions will employ an intent-to-treat approach. Hence, patients will be analyzed according to the treatment group to which they are assigned, even if they did not receive the intended treatment or received only a portion of it.

B. Safety Hypothesis

The hypothesis is that adverse event rates between regimens will be comparable.

Safety Measures

Safety measures will be the number and category of reported adverse events

C. Secondary Research Hypotheses

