.50	.35	206/arm	237/arm	711
.45	.30	197/arm	226/arm	678
.40	.25	185/arm	213/arm	639
.35	.20	168/arm	193/arm	579

Based on these results, it is concluded that a study with 226 patients/arm is adequately powered to detect an absolute difference of 15% in live birth rates between two treatment arms, given the best estimates of success rates from the available literature.

A continuity correction was not applied to the sample size estimates for the chi-square test statistic. Such a correction is not necessary due to the expected size within each cell (32).

NICHD Reproductive Medicine Network
 PPCOS-Pregnancy in Polycystic Ovary Syndrome Protocol

6. Total Sample Size

The study will include 678 patients (226 per treatment arm).

C. Allocation of Intervention

1. Timing

A timeline is provided below:

Figure 1: Study Overview

Time line (~weeks)	-4 to 0	1	1-30	~~30-70
Study Phase	Consent PCOS Screen	Progestin withdrawal and Randomization		Pregnancy
Treatments	None- Complete infertility evaluation as necessary	Treatment Arm 1	Metformin XR	None-Collect pregnancy outcome data
		Treatment Arm 2	Clomiphene citrate	
		Treatment Arm 3	Metformin XR/Clomiphene citrate	
Visits	1 or more visits	2-30 (maximum weekly visits for 6 ovulatory cycles)		As necessary

2. Method

a. Randomization Scheme

Six hundred seventy-eight (678) women will be randomized to one of the three treatment conditions. Using a 1:1:1 treatment ratio, there will be 226 women assigned to each treatment arm. The scheme will be a stratified randomization with permuted blocking within each stratum. Stratification variables will be site and prior exposure to either

NICHD Reproductive Medicine Network
PPCOS-Pregnancy in Polycystic Ovary Syndrome Protocol
clomiphene citrate or metformin XR. The DCC statistician will generate the randomization scheme for the study. Because this is double-blind study, the randomization scheme (including block size) will not be disclosed to the RMN investigators or staff, including the Lead Investigators. Unless otherwise specified, treatment arm data will be presented in a blinded fashion within DSMB reports.

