Adverse Event Analysis: Adverse events will be categorized and percentage of patients experiencing adverse events and serious adverse events during the treatment period will be detailed. Chi-square tests will be performed to examine differences in the proportion of total and categories of adverse events within each treatment arm. For each DSMB report, a list and summary of the reported adverse events will be presented in a blinded fashion, unless otherwise formally requested.

C. Secondary Efficacy Measures

Although not powered to address the secondary outcome parameters, such analyses may provide important pilot data for powering future studies. Multiple logistic regression models will be used in analyses of secondary efficacy measures to evaluate the predictive value of treatment condition, clinical site (if needed), prior exposure to either clomiphene citrate or metformin XR, body mass index, and other explanatory variables on the secondary binary outcomes (e.g., abortion, ovulation). Generalized estimating equations approach will be used if there are multiple outcomes (eg., multiple ovulations) per patient to account correlation within patient. Examples of potential explanatory variables and covariates are: clinical site, prior exposure to either clomiphene citrate or metformin XR, body mass index, age, among others, total testosterone, insulin, proinsulin, and glucose values. Cox proportional hazards models and a Kaplan-Meier method will be applied to compare time to event (eg., cycles to first ovulation, cycles to first conception, cycles to pregnancy, weeks from viable pregnancy to live birth) between the treatment groups.

NICHD Reproductive Medicine Network
PPCOS-Pregnancy in Polycystic Ovary Syndrome Protocol

Due to the exploratory nature of these analyses, the level of significance for the secondary analyses will be set at 0.05 (two-tailed) to reduce the Type II error rate.

Definition of Secondary Measures

- Two different spontaneous abortion rates will be computed. The first is the number of spontaneous abortions over the number of patients who have conceived (defined by positive serum HCG) and the second is the number of spontaneous abortions over the number of patients who are pregnant (defined by detection of fetal heart beat).

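### Comparable adverse event rates are hypothesised, but the plan has only tests for a difference, and the treatment-of-choice wording relies on the absence of significant differences

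*Protocol*

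**What the plan says.** Section III.B gives the safety hypothesis: "The hypothesis is that adverse event rates between regimens will be comparable". It attaches no definition of comparable and no margin.

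Section V.B gives the analysis. For description, the "percentage of patients experiencing adverse events and serious adverse events during the treatment period will be detailed". For inference, "Chi-square tests will be performed to examine differences in the proportion of total and categories of adverse events within each treatment arm". I read the last phrase as a comparison between arms. The opening of section V adds "All statistical tests will test non-directional hypotheses" and "The level of significance will be set at 0.05 for primary analyses and 0.05 for secondary analysis"; no separate level is given for safety.

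Section IV.B.4 brings adverse events into the interpretation of the trial. Under (a), if the combination beats the single agents, then "barring significant differences in adverse events, combination therapy becomes the treatment of choice". Under (b), where the single agents differ from each other, "we expect that metformin would become the treatment of choice, barring substantial differences in adverse events". One clause turns on *significant* differences and the other on *substantial* ones. Neither word is defined.

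The trial is sized in IV.B.5 for live birth only. Section IV.C.2 fixes the arms: "Using a 1:1:1 treatment ratio, there will be 226 women assigned to each treatment arm".

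**The concern.** A test of no difference can count against comparability but cannot count for it. A large p-value is what one sees when the rates are alike, and also when they differ and the trial is too small to show it. Here the hypothesis is comparability, the only test is one for a difference, and the absence of a significant difference clears the way for a treatment recommendation. The rarer the event, the easier that condition is to meet, whatever the truth.

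The protocol's own expectations also sit badly with blanket comparability. Section IV.J expects gastrointestinal symptoms to be about 30% more frequent on metformin XR than on placebo. Section IV.B.2 takes it that the combination brings the side-effect risks of both drugs. What a reader needs is the size of any excess and the largest excess the data leave open. The protocol does not commit to showing either.

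**Working it through.** **1. The stated sizing reproduces, and it is for live birth only.** Inputs (IV.B.5): 45% vs 30%, two-sided alpha 0.025, power 80%, no continuity correction.

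n = [z(0.9875)·√(2·p̄·(1−p̄)) + z(0.80)·√(p1(1−p1) + p2(1−p2))]² / (p1−p2)²

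With p̄ = 0.375, z = 2.241 and 0.842: n = [2.241·√0.46875 + 0.842·√0.4575]² / 0.15² = 196.7, so 197 per arm, as stated. The dropout step is 197 × 1.15 = 226.55, stated as 226. No safety quantity enters the calculation.

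**2. Chance of missing a true doubling of an uncommon event.** Inputs: 226 vs 226 (IV.C.2), uncorrected Pearson chi-square, two-sided 0.05 (section V, assumed to apply to safety). The comparator rates are my assumptions, because the protocol gives no SAE rate. The miss rate is 1 − power, from full enumeration of both binomial distributions.

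| Comparator → doubled rate | Power | Miss rate |
|---|---|---|
| 1% → 2% | 12.5% | about 87% |
| 2% → 4% | 23.7% | 76% |
| 3% → 6% | 33.4% | 67% |
| 5% → 10% | 52.6% | 47% |
| 10% → 20% | 85.6% | 14% |

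Hand check at 3% vs 6% by the normal approximation: the null standard error is √(2·0.045·0.955/226) = 0.01950, and the alternative is √((0.03·0.97 + 0.06·0.94)/226) = 0.01945. Then (0.03 − 1.96·0.01950)/0.01945 = −0.42, which gives power of about 34%, in line with the table. By the same approximation, power reaches one third at a comparator rate of 2.97%. So a miss rate of two in three or more requires a rate of about 3% or lower.

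**3. Sensitivity.** If the chi-square is one three-arm test on 2 degrees of freedom and one arm is doubled, simulated power at 1%, 2%, 3%, 5% and 10% is 13.8%, 24.9%, 36.0%, 56.7% and 89.3%, which is slightly better. With 192 evaluable per arm (226 × 0.85), the two-arm miss rate at 3% rises to 71%. The pattern does not change.

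**4. What an interval shows that the test does not.** Take 5 vs 11 women with an event out of 226 each, that is 2.2% vs 4.9%, a difference of 6/226 = 2.7 points. The chi-square is 2.33, p = 0.127, not significant. The Newcombe 95% interval for the difference is −0.9 to +6.5 points, so an excess of 6 points is still compatible with the data. With 5 vs 5, the interval is ±3.1 points: even equal counts exclude only an excess above about 3.1 points.

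**The case against.** There are four serious objections.

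*Nothing in the protocol says that p > 0.05 proves comparability.* That is correct. A reader might infer from III.B, V.B and IV.B.4(a) that a combination which doubles serious harm would usually be passed as comparable and recommended. The documents do not support that. The clause in IV.B.4(a) is interpretive text in the sample-size section, nothing ties it formally to the test in V.B, and *significant* may be ordinary usage, since the parallel clause says *substantial*. The recommendation also first requires superior efficacy, which IV.B.2 demands because the combination is presumed to carry added side effects. What stands is narrower: the three passages fit together badly, and the natural reading of IV.B.4(a) gives weight to a null test.

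*The SAE figures concern a test that is not named.* Also correct. V.B commits to SAE percentages and applies chi-square tests to total adverse events and their categories. The figures are therefore conditional, and they apply equally to any uncommon category. For common categories the test is strong: 20% vs 40% is missed about 0.3% of the time. If SAEs are not tested at all, the clause in IV.B.4(a) has no stated SAE criterion, which is no better.

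*Two misses in three or more is not established.* A reader might take that as a general property of the trial. It depends on a comparator rate of about 3% or less. The protocol gives no rate, and its SAE definition (IV.I) is broad, extending to anything the site investigator deems serious. At 5% the miss rate is about one in two, and at 10% about one in seven.

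*Few efficacy trials are sized for rare harms, and interval reporting can be left to the analysis plan.* Fair as far as it goes. The trial need not be larger, and the absence of intervals alone would not be a finding. But the hypothesis, the test and the interpretive clause are all fixed in the protocol, and an analysis plan that added intervals would leave III.B and IV.B.4 as they are.

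**Conclusion.** The point holds as a mismatch between hypothesis, test and interpretation. Comparability is hypothesised, only difference tests are specified, and the absence of significant adverse event differences is a condition for naming the combination the treatment of choice.

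Its size depends on event frequency. It matters most for events at about 3% or below in the comparator arm and little for common ones. The figures assume 226 analysed per arm, an uncorrected two-sided 0.05 chi-square and a true doubling. The base rates are assumptions, and the use of the test on SAEs is an inference from V.B.

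The primary live-birth analysis is not affected. The safety statement that accompanies any recommendation is, and it should be corrected before the data are unblinded.

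**What to change.** - **V.B:** report the risk difference with a 95% confidence interval for total adverse events, adverse event categories and SAEs, for the combination against each single agent and for the two single agents against each other. State that a non-significant test will not be read as evidence of comparability. The chi-square tests may stay as a supplement.
- **III.B:** reword as estimation, for example: adverse event and SAE risks will be compared between regimens by risk differences with 95% confidence intervals.
- **IV.B.4(a) and (b):** replace *significant* and *substantial* with one common criterion that refers to these intervals and their upper limits. The sponsor chooses the criterion.
- **Margin:** needed only if the sponsor wishes to claim comparability, in which case it should be set before unblinding. Otherwise, report the largest excess that is not excluded.

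The cost is protocol and analysis-plan wording, plus intervals from data already being collected. It needs no extra patients or visits. The price is a less favourable safety statement: with 5 vs 5 SAEs, the trial could say only that an excess above about 3.1 points is excluded.
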